#### Choice of outcomes

The 5 patient-centered comparators will be the outcomes for Aim 2. The comparators were selected because quality of health and PCP care received might impact patients' long-term outcomes. They then become the "exposure" for the remaining Aims. For Aims 3 and 4, the transition outcome was selected because the ability to perform functional activities, avoidance of institutionalization, and death are meaningful and important to people.

#### **Analytic Methods (General)**

**Approach to Community-Based Participatory Research:** PWD have already contributed substantially to this proposal, forging strong partnerships between stakeholders and scientists. PWD helped establish Aims and Hypotheses, started building necessary research infrastructures within VAI's extensive and well-established volunteer network, drafted questions for use in focus groups, tested focus group procedures within VAI, evaluated and interpreted preliminary findings, contributed to the management plan, and advised on human subject protection issues. Stakeholders will participate in all aspects of CBPR design. In total, there will be 8 VAI groups, 3 Urban (in-person) groups, and 4 Clinician groups recruited for these tasks whose participation will address all 4 Aims. CBPR methods will thus secure knowledge from "inside experts" living with a variety of disabilities.

"Medicalized" disabilities tend to be defined negatively as personal deviation from "the normal or ideal." Stakeholders with disabilities will be engaged to move inferences about disability beyond "medicalization" thus embracing the social model of disability. Stakeholder involvement offers the "most authentic voices" about external barriers to healthcare and articulates factors PWD, their families, and clinicians believe threaten their abilities to maintain independence and autonomy. Aim 1 (fully qualitative) is preparatory for all other Aims. Aims 2, 3, and 4 each begin with quantitative inquiry followed by clarifying and continued qualitative stakeholder input.

**Reducing low literacy barriers:** About 14% of the population cannot do simple reading tasks such as locating an expiration date on a driver's license or signing their name. To reach our stakeholders, prior to beginning the Aims, one VAI and one Urban group will help staff rewrite focus group questions to enhance readability for low literacy participants. The optimal readability goal will be set between the 4th and 6th grades as measured by a Flesch-Kincaid readability score. This score interprets comprehension difficulty of text according to US educational reading grade level by determining average sentence length and number of syllables and the degree to which proper nouns and structurally complex sentences are included.

#### **Preliminary findings:**

Our preliminary work established strong partnerships between stakeholders and scientists. The stakeholder and scientist teams contributed equally to this proposal, generating ideas, creating and finalizing the specific Aims, establishing the initial protocol, interpreting preliminary findings, running groups in Second Life, and establishing a shared timeline.

**Qualitative and CPBR:** The stakeholder and scientific teams had multiple group meetings in Second Life where they worked on protocol design, interpretation of the preliminary results, and all other project preparations. The PI and stakeholder consultant ([name] and [name]) ran 4 pilot peer support groups in VAI on the inaccessibility of medical equipment and

PRINCIPAL INVESTIGATOR (LAST, FIRST, MIDDLE): [name]

services (see example of de-identified “chat” in Appendix C). The “public abstract” was written iteratively partnering between the stakeholder and quantitative analytic teams. We reached our readability goal at or below the 6th grade level. Readability was estimated by the Flesch-Kincaid Grade Level score, which was approximately at grade 5.5 based on the USA educational system.

**Quantitative:** Using MCBS data from 3 panels active at the time of the Fall interview in 2005 (N=10,399) and with complete information, we applied a multinomial logistic regression model studying 1-year transition outcomes (2006 on the 4-level transition outcome with no change in function being reference). The global quality comparator was most consistently associated with outcome transition. Poorer perceived healthcare was significantly associated with 1-year, functional deterioration, institutionalization, and mortality (all p-values ≤0.03). Poorer perceived healthcare quality was strongly associated with functional improvement (p=.0001). Both functional improvement and deterioration were strongly associated with poorer access (both p<.0001). Perceptions of poorer access were also associated with death at 1 year (p=.02).

The PCP quality comparators were less strongly related to 1-year transitions. Poorer PCP interpersonal skills were associated with functional deterioration (p=.01) and 1-year mortality (p=.003). Patients’ perceptions of poorer PCP interpersonal skills were marginally associated to institutionalization (p=.07). Poorer quality of information provision was related to institutionalization (p=.04). These findings provide powerful support for this study.

**Stakeholder interpretation:** Stakeholders found all findings logical except linkage between poorer perceived healthcare access and quality and functional improvement. They had the following thoughts and questions: Being angry with poor access and low quality healthcare might motivate functional improvement. Those who improved functionally might be more motivated to fight for better care. Will these findings persist after statistical adjustment and analyses across a decade and timeframe of 3 years? What other factors, potentially discoverable through stakeholder engagement, might explain this startling finding?

**AIM 1: Where do we see the problems?** Aim 1 seeks to uncover themes related to the 5 comparators and stakeholders’ perceptions on whether or not they experience healthcare and PCP quality problems and if those problems impact transition outcomes. PWD, PWOD, and families, in VAI and Urban groups, will address the following kinds of questions in a focus group format: *How does access and quality of healthcare received differ for PWD and PWOD? How does poorer quality healthcare impact risks of functional decline, institutionalization, or death?* The Clinician groups will address identical questions but relative to their clinical practices.

Six focus groups (3 VAI, 1 Urban, and 2 Clinician) will participate. Participants from Second Life (VAI and Clinicians) will be assured that their off-screen identities will remain confidential. Once people provide informed consent, they will be given entry into a private chat room on VAI property at a specific date and time. All of the focus groups will be led by a stakeholder co-investigator with personal knowledge about living with disability. The group leader’s role will be to pose questions in a standardized manner, moderate the discussion, move the discussion along, and keep the discussion safe for all participants. (See draft instructions for stakeholder focus groups in Appendix A). Prior to participation, each participant will be asked to complete a survey about disability(s) and life circumstance (See draft Appendix B). For groups in the virtual world, true identities will be masked behind created avatars (personas that individuals choose to represent themselves); in face-to-face Urban groups, members and their disabilities are known to each other. Text-to-speech software will be available to those who have low literacy.

Participation in the SL focus groups will generate “chat” in the form of typed dialogue (see Appendix C for an example). Participants’ characteristics (derived from the pre-group questionnaire) will be linked to their screen or avatar name (but not their actual identity). The

PRINCIPAL INVESTIGATOR (LAST, FIRST, MIDDLE): [name]

dialogue will be downloaded into document form and entered into QSR NVivo 10.0 for coding and analysis. The Urban group will use the same discussion guide as in the SL groups. Groups will be conducted in a private room. Because in-person focus groups are, by nature, only semi-private, we cannot assure confidentiality, but we will ask all group members to respect the confidentiality of group participants. Individual identities will not be revealed outside the group. All focus group results will be reported in the aggregate and we will not link an individual's name with anything s/he said. In-person focus group proceedings will involve a captionist as an ADA accommodation for deafness. This automatically generates a verbatim transcript which will be entered into NVivo 10.0 software along with chat from the SL groups for coding and analysis.

**Data analysis:** We will use a modified grounded theory approach in the analysis. The investigators will develop a coding structure and a coding dictionary based upon a close reading of the transcripts. All transcripts will be double-coded by project staff from the Mixed Methods Research Lab (MMRL) and from VAI. Once the data are coded, the software will allow us to generate queries to identify the context in which key ideas emerge. The software will also enable us to conduct inter-rater reliability analyses (described below). Areas of content divergence between thematic and quantitative findings will be hypothesis generated. Based upon our experience, these focus groups should be adequate to achieve saturation (where no new themes are emerging from the data). Once we have formed a preliminary theory about the data we have collected, we will use the technique of "member checking" where we will return to a subset of the original group of respondents to obtain feedback on our analysis. Procedures are detailed in the protocol (project plan and timeline).

#### ***Stakeholder input to Aims 2, 3, and 4: discuss emerging "quantitative" findings***

Stakeholder groups will join researchers in interpreting findings during Aims 2 and 3. Tables and figures illustrating results will be presented to 3 VAI, 1 Urban, and 1 Clinician stakeholder groups. First, we will determine whether stakeholders understand the presentation by asking, "How would you explain these findings to a friend or family member?" Then we will ask questions such as, "What do you think explains these results?" "Tell us how to show these findings more clearly?" "What makes sense to you, and why?" "What does not make sense, and why?" Information will be applied to enhance clarity of findings for dissemination. Stakeholder concepts (particularly the "Do these findings make sense?" questions) will be combined with quantitative findings and the literature in formulating the **Patient-Informed Surveillance Tool**.

#### ***Stakeholder group member checking - did the researchers get it right?***

The growing bank of stakeholder knowledge will help determine if we have asked the right questions and if answers make sense. We may suppress or choose not to include certain predictive associations between comparators and outcomes that appear counter-intuitive, unexplainable, or we believe might encourage adverse quality incentives when building the **Patient-Informed Surveillance Tool**. The association of perceptions of poorer quality with functional improvement is an example from preliminary work that might be presented but not included in the final surveillance tools.

***Stakeholder groups will inform the simulations and final conclusions helping researchers interpret all findings.*** We will ask 2 VAI, 1 Urban, and 1 Clinician group to discuss strategies to encourage changes in the healthcare system targeted to enhancing the wellbeing of PWD. We will present scenarios illustrating findings from the statistical simulations. The following example illustrates the types of questions to be asked using preliminary findings.

***"Our research shows that when people with disabilities receive coordinated and high quality healthcare, their disabilities are less likely to get worse. How should healthcare be improved? How could your doctor implement these improvements?"*** Materials from these groups will be analyzed as described in Aim 1 with quotes extracted to enhance clarity of findings.

PRINCIPAL INVESTIGATOR (LAST, FIRST, MIDDLE): [name]

**What is the evidence?** Our goal for the quantitative component of Aims 2-4 is to provide evidence for existence or non-existence of disability-related disparities in healthcare and, if present, to quantify their outcome implications among PWD compared to PWOD. Gaps as perceived by stakeholders (according to the 5 comparators) will be quantified using the MCBS. Results will be presented to groups of PWD in simplified illustrative scenarios and to clinicians in scientific presentation format.

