The **Patient-Informed Surveillance Tool** will be developed in three steps using an approach we applied recently. (1) assess the quality of candidate predictors through the combined input of stakeholder and researcher recommendations with demonstrated bi-variable associations  $p < .20$ ; (2) beginning with a regression containing all candidate covariates, estimate a parsimonious model by using backward selection to remove all candidate variables at  $p > .05$ ; (3) develop a simply applied point-scoring system from the estimates associated with each variable in the final model by dividing each significant  $\beta$ -coefficient by the lowest significant  $\beta$ -coefficient and rounding to the nearest integer. A value of "0" will be assigned to non-significant  $\beta$ -coefficients. Depending on demonstrated affect modification, working-aged and elderly beneficiaries might be included in separate Tools. The final set of **Patient-Informed Surveillance Tools** will group sub-populations by outcome expectation as determined by perceptions according to each comparator adjusted for ADL or IADL stage, living circumstances (i.e., family members who might provide care, home accessibility, etc.), diagnoses, socioeconomic status (i.e., income, education, etc.), comparator status, and other covariates. The final selection of variables in the Tools will be informed by stakeholder input (see above) as well as statistical findings.

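### Associations may be left out of the Patient-Informed Surveillance Tool after results are seen because they look counter-intuitive or unexplainable, so the Tool can be selected on direction of effect

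*Combined protocol and SAP*

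**What the plan says.** The section on stakeholder member checking sets the rule: "We may suppress or choose not to include certain predictive associations between comparators and outcomes that appear counter-intuitive, unexplainable". The same sentence adds a third ground, "or we believe might encourage adverse quality incentives when building the" Tool. It then gives the link between poorer perceived quality and functional improvement as an example that "might be presented but not included in the final surveillance tools".

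Three other places fix how the rule works.

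- **Stakeholder input to Aims 2, 3 and 4.** Tables and figures of results go to the stakeholder groups. Their answers on whether the findings make sense are then combined with the statistics and the literature in forming the Tool.
- **Data Analysis, development of the Tool.** Candidates come from stakeholder and researcher recommendations with a bivariable p<.20. Backward selection removes those with p>.05, and the surviving coefficients become integer points. The paragraph then adds: "The final selection of variables in the Tools will be informed by stakeholder input", alongside the statistical findings.
- **Preliminary findings.** The one-year 2005-2006 models are reported with this reaction: "Stakeholders found all findings logical except linkage between poorer perceived healthcare access and quality and functional improvement".

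Choice of Study Design describes the Tool as the project's final deliverable.

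**The concern.** Two of the three grounds for exclusion depend on the result itself. Nobody can call an association counter-intuitive before seeing which way it points, or unexplainable before trying to explain it. The plan places that judgement after results are shown and carries it into the final choice of variables. It gives no definition of either word, no log of exclusions, and no requirement to build or report the Tool without them.

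A Tool assembled this way can agree with the project's hypothesis partly because disagreeing associations were taken out. Its users would be health systems and policy makers monitoring disparities. They could not tell whether a missing link was absent from the data, removed by the p-value rule, or removed because of its direction.

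**Working it through.** The plan states no figure for this rule, so there is nothing to reproduce. Two checks apply.

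**1. What the rule would do to the preliminary results.** The inputs are all associations reported at p<.05 under Preliminary findings.

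| Poorer rating on | Outcome | p quoted | Direction |
|---|---|---|---|
| Quality | Deterioration | ≤0.03 | expected |
| Quality | Institutionalization | ≤0.03 | expected |
| Quality | Death | ≤0.03 | expected |
| Quality | Improvement | .0001 | counter |
| Access | Improvement | <.0001 | counter |
| Access | Deterioration | <.0001 | expected |
| Access | Death | .02 | expected |
| PCP interpersonal skills | Deterioration | .01 | expected |
| PCP interpersonal skills | Death | .003 | expected |
| PCP information | Institutionalization | .04 | expected |

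Expected direction means poorer care with a worse outcome. The link between interpersonal skills and institutionalization (p=.07) misses the cut and is not counted.

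- Total: 10. Expected: 3 (quality) + 2 (access) + 2 (interpersonal) + 1 (information) = 8. Counter: 2.
- Share in the expected direction with all kept: 8/10 = 80%.
- Share with the two counter-direction links left out: 8/8 = 100%.

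The two counter-direction links are exactly the two that stakeholders found illogical. Three quality p-values are given only as a bound, so a full ranking is not possible. At p=.0001 and p<.0001, the two links are still among the smallest values quoted, so the p-value rule alone would be unlikely to remove them if they persisted.

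**2. What a direction filter does to a null coefficient.** Assume an approximately normal estimate with no true effect, a two-sided 0.05 cut, and a filter that always drops the unexpected direction.

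- Without the filter: probability 0.025 of being retained in each direction, so retained estimates average 0.
- With the filter: probability 0.025 of being retained, always in the expected direction. The average retained estimate is φ(1.96)/0.025 = 0.05845/0.025 = 2.34 standard errors.

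This shows the mechanism only. It does not estimate the distortion in this study, because the plan makes exclusion optional.

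**The case against.** The strongest reply has five parts.

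- **Nothing is committed.** The wording is permissive, covers only certain associations, and offers the quality-improvement link as an example. This stands. A reader might infer that the plan has already decided to drop that link, and the text does not say so. What remains is discretion with no criterion attached.
- **The findings are not hidden.** The example may be presented. Aim 3 reports relative risk ratios for every transition state, improvement included, and Aim 4 simulates improvement with the other states. The replication section promises tables, tested hypotheses and code. This also stands, and it confines the point to the Tool. But presenting the example is optional, and no section requires a list of what was left out of the Tool or why.
- **The preliminary signal is provisional.** Stakeholders asked whether it will survive adjustment, ten years of data and three years of follow-up. That is a sound question. It favours testing the association in the full data over having a route to remove it for being unexplained.
- **Stakeholder judgement is the purpose of participatory research.** Agreed. Stakeholders can propose candidates, interpret and annotate without removing terms by direction.
- **Avoiding perverse incentives is legitimate.** Agreed. A surveillance score that credited poor perceived quality with improvement might reward it, so the named example could qualify on this ground. That ground does not need the other two beside it.

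A reader might also suspect that the improvement link arises because people at stage 0 cannot improve. That is a separate question. The general approach to analysis already controls every model for baseline ADL or IADL stage.

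**Conclusion.** The point holds for the Tool. As written, the plan permits result-driven exclusion by direction of effect, with no prior criterion and no required disclosure. On the preliminary results, using it for both links that stakeholders found illogical would move the expected-direction share from 8 of 10 to 8 of 8. That count assumes that both links are excluded and that the final data resemble the 2005-2006 results. The plan guarantees neither.

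A reader might go further and infer that the Tool would overstate the net harm of poor quality by some definite factor. The documents do not support this, for three reasons.

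- They give no transition base rates or estimated ratios.
- They do not say that the Tool is a single multinomial model or that it outputs state probabilities. They describe an integer point score from a regression.
- Any factor is driven by the assumed inputs. Take assumed base rates of 78% stable, 6% improved, 12% deteriorated and 4% other, and an assumed ratio of 1.3 for deterioration. Measure the change in deteriorated minus improved. Without the improvement term the change is (15.6 − 6)/103.6 − 6% = +3.27 points. With an improvement ratio of 1.3 it is (15.6 − 7.8)/105.4 − 6% = +1.40 points, an overstatement of about 2.3-fold. At improvement ratios of 1.1, 1.2 and 1.5 the factor is 1.24, 1.62 and about 17, and at 1.6 the full-model change is negative.

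Nor does the rule bias the Aim 3 ratios or the Aim 4 simulations, since it is worded for building the Tool.

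**What to change.** 1. In the member-checking section, delete counter-intuitive and unexplainable as grounds for exclusion.
2. Leave the p-value selection described for the Tool in place, and state that direction of effect is never a reason for removal. Bring the closing sentence on final variable selection into line with this. There is no need to force all five comparators into the Tool whatever their p-values, which would overturn the plan's own selection step.
3. Keep the adverse-quality-incentive ground. Have the governance group list and date any such exclusion, with its reason, before the late (full-data) analyses. The 2005-2006 results are already known, so listing before any model is fitted is no longer possible.
4. Report each excluded association with its estimate and reason, and show the Tool's discrimination and calibration with and without the exclusions.

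The cost is a few sentences of plan text, one dated list and one extra model comparison. The downside is that the Tool may carry an association that stakeholders find hard to explain, which can be handled by annotation.

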#### **Choice of data for quantitative analyses and Description of Data Sources**

The MCBS is conducted by the Centers for Medicare and Medicaid Services (CMS) through in-person beneficiary or proxy interviews. Respondents are sampled from the Medicare enrollment file to be representative of the Medicare population as a whole. Sample persons are interviewed three times a year for a maximum of four years forming a continuous profile of each individual's personal health care experience. Aims 2, 3, and 4 will apply a decade of data from the MCBS. The MCBS sample was selected for the qualitative aspects of Aims 2, 3, and 4 because these data provide the means to quantify the prevalence of disparities within the Medicare population and any associated outcome burden at the societal level. Also, derivation of the **Patient-Informed Surveillance Tool** within MCBS data will facilitate its potential implementation within Medicare as a means to monitor disparities and outcomes. The oldest old (80 and over) and the young disabled (between the ages of 21 and 64) are oversampled to permit more detailed analyses of these sub-populations. The MCBS applies a rotating panel survey design. A rotating panel will be followed for 12 interviews. There are four panels active at any one time. Each has approximately 4,000 sample persons. New panels introduced each year in the fall round will replace the oldest panel retired the following summer. This project will use the Access to Care files from the MCBS which include all variables needed in the analyses.

**The Study Sample:** An Access to Care file is released within 2 years of the survey. We plan to request 10 panels entering at the time of their fall interview in 2000-2009. Access to Care files in the following 3 fall interviews (2010-2012) will serve to track 1, 2, and 3 year transition outcomes. The sample will include all fee for service and Health Maintenance Organization (HMO) Medicare beneficiaries 21 years of age and older. Those living in institutions at the time of their initial interviews will not be included since institutionalization is an outcome state.

**1. Variable Definition and Measurement (Quantitative).** All variables are available in the MCBS Access to Care files.

